## List of Abbreviations

Abbreviation	Definition
Ab	antibody
AE	adverse event
AESI	adverse event of special interest
ALP	alkaline phosphatase
ALT	alanine aminotransferase
AR	adverse reaction
ARDS	acute respiratory distress syndrome
AST	aspartate aminotransferase
bAb	binding antibody
BD	booster dose
BMI	body mass index
BP	blood pressure
CI	confidence interval
COVID-19	coronavirus disease 2019
DHHS	Department of Health and Human Services
eCRF	electronic case report form
eDiary	electronic diary
ELISA	enzyme-linked immunosorbent assay
FIO2	fraction of inspired oxygen
GM	geometric mean
GMFR	geometric mean fold rise
GMC	geometric mean concentration
GMR	geometric mean ratio
IgG	immunoglobulin G
IP	investigational product
LLOQ	lower limit of quantification
LOD	limit of detection
MAAE	medically-attended adverse event
MedDRA	Medical Dictionary for Regulatory Activities
mITT	modified intent-to-treat
mRNA	messenger ribonucleic acid
MSD	Meso Scale Discovery
nAb	neutralizing antibody
NP	nasopharyngeal
PaO2	partial pressure of oxygen
PCR	polymerase chain reaction
PP	per-protocol
PT	preferred term
RT-PCR	reverse transcriptase polymerase chain reaction
S	Spike
SAE	serious adverse event
SAP	statistical analysis plan

Abbreviation	Definition
SARS-CoV-2	Severe Acute Respiratory Syndrome coronavirus
SD	standard deviation
SOC	system organ class
SOT	solid organ transplant
SpO2	oxygen saturation
SRC	Safety Review Committee
TEAE	treatment-emergent adverse event
ULOQ	upper limit of quantification
UPCR	urine protein to creatinine ratio
WHO	World Health Organization
WHODD	World Health Organization drug dictionary

## 1. Introduction

This statistical analysis plan (SAP), which describes the planned analyses for Study mRNA-1273-P304, is based on the most recent approved clinical study protocol, including Amendment 4, dated 20-December-2021 and on the most recent approved electronic case report form (eCRF), dated 28-Feb-2022.

In addition to the information presented in the statistical analysis plan section of Protocol Amendment 4 (Section 8), which provides the principal features of analyses for this study, this SAP provides statistical analysis details/data derivations. It also documents modifications or additions to the analysis plan that are not “principal” in nature and result from information that was not available at the time of protocol finalization.

Study mRNA-1273-P304 is a Phase 3b open-label study to evaluate the safety, reactogenicity, and immunogenicity of messenger ribonucleic acid (mRNA)-1273 Severe Acute Respiratory Syndrome Coronavirus 2 (SARS-CoV-2) vaccine in adult solid organ transplant recipients and healthy controls.

PPD Biostatistics and programming team, designee of Moderna Biostatistics and Programming department, will perform the statistical analysis of the safety, reactogenicity, and immunogenicity data; SAS Version 9.4 or higher will be used to generate all statistical outputs (tables, figures, listings, and datasets). The SAP will be finalized and approved prior to the primary analysis clinical database lock. If the methods in this SAP differ from the methods described in the protocol, the SAP will prevail.

In this document, subject, patient, and participant are used interchangeably; injection of investigational product (IP), dose, study vaccine, study IP, and study injection are used interchangeably; Booster injection, booster vaccine, booster dose (BD), and booster are used interchangeably.

## 2. Study Objectives

### 2.1. Primary Objective

The primary objectives for Part A are the following:

- To evaluate the safety of 100 µg mRNA-1273 administered in 2-dose or 3-dose regimens
- To evaluate the reactogenicity of 100 µg mRNA-1273 administered in 2-dose or 3-dose regimens
- To evaluate serum neutralizing antibody (nAb) responses to doses of 100 µg mRNA-1273 obtained 28 days after second or third dose

The primary objectives for Part B are the following:

- To evaluate the safety of the 100 µg BD of mRNA-1273
- To evaluate serum nAb responses elicited by the 100 µg mRNA-1273 obtained 28 days after the BD

## **2.2. Secondary Objectives**

The secondary objectives for Part A are the following:

- To evaluate the persistence of the immune response to 2 or 3 doses of 100 µg mRNA-1273, as assessed by the level of anti-SARS-CoV-2 Spike (S) specific binding antibody (bAb) through 1 year after dose 2 or dose 3
- To evaluate the persistence of the immune response to 2 or 3 doses of 100 µg mRNA-1273, as assessed by the level of nAb through 1 year after dose 2 or dose 3
- To describe the incidence of asymptomatic SARS-CoV-2 infection after mRNA-1273 vaccination in adult solid organ transplant (SOT) recipients and healthy adult participants with negative SARS-CoV-2 at baseline
- To describe the incidence of coronavirus disease 2019 (COVID-19) after vaccination with mRNA-1273 in SOT recipients and healthy participants
- To describe changes in liver and renal function through laboratory tests over time in SOT recipients after vaccination with mRNA-1273 vaccine
- To describe changes in immunosuppressant medications in SOT recipients after vaccination with mRNA-1273 vaccine

## **2.3. Exploratory Objectives**

The exploratory objectives for Part A are the following:

- To evaluate the genetic and/or phenotypic relationships of isolated SARS-CoV-2 strains to the vaccine sequence
- To characterize the clinical profile and immune responses of participants with COVID-19 or with SARS-CoV-2 infection
- To describe the incidence of asymptomatic SARS-CoV-2 infection after mRNA-1273 vaccination in adult SOT recipients and healthy adult participants with serologic evidence of infection at baseline
- To assess, in a subset of SOT recipients who received 3-dose regimen and healthy participants who received 2-dose regimen, SARS-CoV-2 S protein-specific T cell responses

- To define, in a subset of SOT recipients who received 3-dose regimen and healthy participants, the epitopes recognized by B cells and antibodies generated in response to mRNA-1273

The exploratory objectives for Part B are the following:

- To evaluate the persistence of the immune response of the BD of mRNA-1273 vaccine (100 µg) as assessed by the level of SARS-CoV-2 S2P specific bAb through 6 months after BD
- To evaluate the persistence of the immune response of the BD of mRNA-1273 vaccine (100 µg) as assessed by the level of nAb through 6 months after BD
- To describe the incidence of asymptomatic SARS-CoV-2 infection after mRNA-1273 vaccination in adult SOT recipients and healthy adult participants with negative SARS-CoV-2 at baseline
- To describe the incidence of COVID-19 after vaccination with mRNA-1273 in SOT recipients and healthy participants
- To describe changes in liver and renal function through laboratory tests over time in SOT recipients after vaccination with mRNA-1273 vaccine
- To describe changes in immunosuppressant medications in SOT recipients after vaccination with mRNA-1273 vaccine
- To evaluate the genetic and/or phenotypic relationships of isolated SARS-CoV-2 strains to the vaccine sequence
- To characterize the clinical profile and immune responses of participants with COVID-19 or with SARS-CoV-2 infection
- To describe the incidence of asymptomatic SARS-CoV-2 infection after mRNA-1273 vaccination in adult SOT recipients and healthy adult participants with serologic evidence of infection at baseline
- To assess, in a subset of SOT recipients and healthy participants who received BD, SARS-CoV-2 S protein-specific T-cell responses
- To define, in a subset of SOT recipients and healthy participants, the epitopes recognized by B-cells and antibodies generated in response to mRNA-1273

### 3. Study Endpoints

Generally, safety objectives are assessed through the evaluation of adverse events (AEs), laboratory test results, and vital signs measurements. Reactogenicity objectives are assessed through the evaluation of solicited local and systemic adverse reactions (ARs).

#### 3.1. Primary Endpoints

The safety of 100 µg mRNA-1273 administered in 2-dose or 3-dose regimens will be evaluated by the following endpoints:

- Unsolicited AEs through 28 days after each injection
- Medically attended adverse events (MAAEs) from Day 1 and throughout the study period
- Serious adverse events (SAEs) from Day 1 and throughout the study period
- Adverse events of special interest (AESIs) from Day 1 and throughout the study period
- AEs leading to discontinuation from dosing and/or study participation (withdrawal) on Day 1 and throughout the study period
- Biopsy-proven organ rejection from Day 1 and throughout the study period

The reactogenicity of 100 µg mRNA-1273 administered in 2-dose or 3-dose regimens will be evaluated by the following endpoints:

- Solicited local and systemic ARs through 7 days after each injection (for unvaccinated participants who received 2 doses of mRNA-1273)
- Solicited local and systemic ARs through 7 days after each injection (for unvaccinated SOT recipients who received 3 doses and SOT recipients previously vaccinated outside the study who received a third booster dose)

The nAb responses to doses of 100 µg mRNA-1273 obtained 28 days after the second dose or third dose will be evaluated by the following endpoints:

- The geometric mean concentration (GMC) of serum SARS-CoV-2-specific nAb after the second dose (Day 57 for unvaccinated participants)
- The GMC of SARS-CoV-2-specific nAb 28 days after dose 3 (Day 113 for unvaccinated SOT recipients and Day 29 for previously vaccinated SOT recipients)

The safety of 100 µg BD of mRNA-1273 will be evaluated by the following endpoints:

- Unsolicited AEs through 28 days after BD injection
- MAAEs throughout the study period

- SAEs throughout the study period
- AESIs, including myocarditis/pericarditis throughout the study period
- AEs leading to discontinuation from dosing and/or study participation (withdrawal) throughout the study period
- Biopsy-proven organ rejection throughout the study period

The reactogenicity of 100 µg BD of mRNA-1273 will be evaluated by the following endpoint:

- Solicited local and systemic ARs through 7 days after BD injection

The nAb responses to 100 µg BD of mRNA-1273 obtained 28 days after the BD will be evaluated by the following endpoints:

- The GMC of serum SARS-CoV-2-specific nAb 28 days after the BD in SOT participants who received the Moderna primary series
- The GMC of SARS-CoV-2-specific nAb 28 days after BD in SOT participants who received mRNA or non-mRNA COVID-19 vaccine primary series outside the study

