
 To define, in a subset of SOT recipients who received 3-dose regimen and healthy participants, the epitopes recognized by B-cells and antibodies generated in response to mRNA-1273 	
 Magnitude and phenotype of S protein-specific B-cells as measured by flow cytometry at Day 1, Day 36, and Day 92 for unvaccinated SOT recipients, at Day 1 and Day 8 for previously vaccinated SOT recipients, and at Day 1 and Day 36 in healthy participants Determination of targeted major antigenic sites and amino acid residues on SARS-CoV-2 S protein

Objectives	Endpoints
Part B – Booster Phase	
Primary Objectives	Primary Endpoints

• To evaluate the safety of the 100 µg BD of mRNA-1273	
• Solicited local and systemic ARs through 7 days after BD injection• Unsolicited AEs through 28 days after BD injection• MAAEs throughout the study period• SAEs throughout the study period• AESIs, including myocarditis/pericarditis throughout the study period• AEs leading to discontinuation from dosing and/or study participation (withdrawal) throughout the study period• • Biopsy-proven organ rejection throughout the study period

• To evaluate serum nAb responses elicited by the 100 µg mRNA-1273 obtained 28 days after the BD	
• The GMT value of serum SARS-CoV-2-specific nAb level 28 days after the BD in SOT participants who received the Moderna primary series• The GMT value of SARS-CoV-2-specific nAb level 28 days after BD in SOT participants who received non-Moderna primary series
Exploratory Objectives	Exploratory Endpoints

• To evaluate the persistence of the immune response of the BD of mRNA 1273 vaccine (100 µg) as assessed by the level of SARS-CoV-2 S2P specific bAb through 6 months after BD	
• The GM value of SARS-CoV-2 S2P specific bAb on BD-Day 1, BD-Day 29 (28 days after BD), BD-Day 181 (6 months after BD)

Objectives	Endpoints

 To evaluate the persistence of the immune response of the BD of mRNA 1273 vaccine (100 µg) as assessed by the level of nAb through 6 months after BD 	
 The GM values of SARS-CoV-2-specific nAb on BD-Day 1, BD-Day 29 (28 days after BD), BD-Day 181 (6 months after BD)

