For unvaccinated SOT recipients (Group A1 and Group A2), laboratory assessments for safety related to kidney function for kidney SOT recipients (serum creatinine, urine protein, and UPCR) and liver function for liver SOT recipients (alanine aminotransferase [ALT], aspartate aminotransferase [AST], alkaline phosphatase [ALP], and bilirubin) will be monitored on Day 1, Day 8, Day 29, Day 36, and Day 57 for SOT recipients who receive 2 doses only (Group A1) and on additional Days 85, 92, and Day 113 for SOT recipients who receive 3 doses (Group A2).

For previously vaccinated SOT recipients (Group A3), laboratory assessments for safety will be monitored on Day 1 (dose 3), Day 8, and Day 29.

After Day 57 (for unvaccinated SOT participants who receive 2 doses [Group A1]) or after Day 113 (for unvaccinated SOT participants who receive 3 doses [Group A2]), or after Day 29 (for previously vaccinated SOT recipients who receive dose 3 [Group A3]), the investigator will review standard-of-care laboratory assessments related to kidney and liver function and report any laboratory-related AEs and suspected or confirmed events of organ transplant rejection until the EOS.

Part B - Booster Phase

Part B is designed to offer participants in Part A, who are at least 4 months from the last dose, the option to request a BD (100 µg) of the prototype mRNA-1273 (Group B2, Group B3, and

Group B5). Part B is also designed to enroll SOT participants who completed primary vaccination series with mRNA or non-mRNA COVID-19 vaccine under the EUA who are at least 4 months from last dose (Table 3). At least 50 SOT recipients who completed primary vaccination series with a non-Moderna COVID-19 vaccine under the EUA (outside of the mRNA-1273-P304 study) will be enrolled in Part B. In case a variant of concern emerges and available data show a decreased immune response after vaccination with the prototype 100 µg BD, the Part B Booster Phase may test or replace the prototype 100 µg BD with a variant-specific mRNA-1273 vaccine (ie, Omicron-specific or mRNA-1273.529).

Table 3: Primary Series Vaccination for Booster Dose Eligibility

Primary Series Vaccine	Primary Series Number of Doses
mRNA COVID-19 vaccine (ie, Moderna, Pfizer)	3 doses
Non-mRNA COVID-19 vaccine (ie, Janssen)	2 doses or at least 1 dose combined with an mRNA COVID-19 vaccine

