#### **6.4.2. Primary Analysis of Neutralizing Antibody Response**

GMC of SARS-CoV-2-specific nAb with corresponding 95% CI will be provided at each time point. The GMC at Day 57 from unvaccinated participants in the 2-dose regimen, the GMC at Day 113 from unvaccinated participants in the 3-dose regimen, Day 29 for SOT participants that are previously vaccinated with Moderna COVID-19 vaccines, and BD-Day 29 for SOT participants that are previously vaccinated with Moderna COVID-19 vaccine/non-Moderna COVID-19 vaccine forms the basis for the evaluation of the primary immunogenicity objective. The GMC at other visits will help address the evaluation of the secondary immunogenicity objective related to nAb levels.

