## **7. Changes from Planned Analyses in Protocol**

Not applicable.

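### SAP 3.1 replaces the protocol's non-Moderna population in the second Part B primary neutralising-antibody endpoint with any outside-study series, and declares no change

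*SAP*

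**What the plan says.** The protocol gives two primary neutralising-antibody endpoints for Part B, in the same terms in the synopsis and in Section 2, Table 1. One is the titre 28 days after the booster in transplant recipients with a Moderna primary series. The other is the "nAb level 28 days after BD in SOT participants who received non-Moderna primary series".

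SAP Section 3.1 keeps the first: "The GMC of serum SARS-CoV-2-specific nAb 28 days after the BD in SOT participants who received the Moderna primary series". Its second is: "The GMC of SARS-CoV-2-specific nAb 28 days after BD in SOT participants who received mRNA or non-mRNA COVID-19 vaccine primary series outside the study".

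SAP Section 6.4.2, which states which geometric means form the basis for the primary immunogenicity objective, refers to "BD-Day 29 for SOT participants that are previously vaccinated with Moderna COVID-19 vaccine/non-Moderna COVID-19 vaccine".

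On precedence, SAP Section 1 says: "If the methods in this SAP differ from the methods described in the protocol, the SAP will prevail". SAP Section 7, on changes from the protocol, reads "Not applicable".

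**The concern.** A primary endpoint is partly defined by who is in it. The protocol splits boosted transplant recipients by the brand of their primary series. SAP 3.1 describes the second group by where the series was given, whatever the vaccine. These are not the same people if anyone received a full Moderna series outside the study, and Group B4 is open to such participants.

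Protocol Section 3.2 expects Part B to yield booster data in both the homologous and the heterologous setting. Under the SAP 3.1 wording, the second primary geometric mean would mix the two. SAP Section 1 presents its departures from the protocol as not principal, and Section 7 lists none. A reader of the SAP would therefore not learn that a primary endpoint population had moved, or whether the move was meant.

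**Working it through.** No stated sample size, power or error rate is involved, so there is no figure in the plan to reproduce. The check is one of classification.

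**Step 1. Who can be in Group B4.** Protocol Table 2 and Section 4.2.1 admit recipients who completed either an mRNA or a non-mRNA series outside the study. For the three-dose route, Table 3 lists "mRNA COVID-19 vaccine (ie, Moderna, Pfizer". Three Moderna doses given elsewhere therefore qualify for B4. SAP 6.1 also lists a 3-Dose Moderna row among boosted transplant recipients.

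**Step 2. Place each type of boosted transplant recipient.**

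| Participant | Protocol | SAP 3.1 as worded |
|---|---|---|
| B2: three Moderna doses in the study | first | first |
| B3: two Moderna doses outside, the third in the study | first | first |
| B4: three Moderna doses outside | first | second; also first, unless the first is read as in-study only |
| B4: three Pfizer doses outside | second | second |
| B4: two Janssen doses outside | second | second |

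Only the third row differs. On either reading of the first endpoint, SAP 3.1 puts these participants in the second endpoint and the protocol does not.

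**Step 3. Compare within the SAP.** Section 6.4.2 uses the protocol's brand split, so Sections 3.1 and 6.4.2 disagree. Section 6.1 lists boosted recipients as overall, three-dose Moderna, three-dose Pfizer and other. No row pools the non-Moderna series, and none pools every series given outside the study. Neither version of the second endpoint has a matching row.

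**Step 4. The enrolment minimum.** Protocol Section 3.1 requires at least 50 recipients with a non-Moderna series in Part B. SAP Section 4.1 states the minimum for any outside-study series, the same rewording as in SAP 3.1.

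**Step 5. Illustration of size.** Let n be the non-Moderna recipients in B4, m the three-dose Moderna recipients in B4, and r the ratio of the Moderna to the non-Moderna geometric mean after the booster. Then:

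- Moderna share of the SAP 3.1 population = m/(n+m).
- SAP 3.1 geometric mean ÷ non-Moderna geometric mean = r^(m/(n+m)).

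The documents give neither m nor r, so both are assumed here. I set n = 50, the protocol's enrolment minimum.

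| m (assumed) | share | r = 0.5 | r = 1 | r = 2 |
|---|---|---|---|---|
| 0 | 0/50 = 0% | 1.00 | 1.00 | 1.00 |
| 10 | 10/60 = 16.7% | 0.89 | 1.00 | 1.12 |
| 25 | 25/75 = 33.3% | 0.79 | 1.00 | 1.26 |
| 50 | 50/100 = 50% | 0.71 | 1.00 | 1.41 |

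These figures illustrate an enrolled population and are not bounds on the analysis. The primary analysis uses the Part B Per-Protocol Immunogenicity Set (SAP 5.3.3). That set drops participants with evidence of earlier infection, non-compliant sampling or relevant major deviations, so the number analysed can fall below 50.

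**The case against.** The strongest reply is that the operative text is already right. Section 6.4.2 says what the primary evaluation rests on, and it follows the protocol. The precedence clause ranks the SAP over the protocol on methods; it does not rank Section 3.1 over Section 6.4.2. A reader might infer from it that the 3.1 wording controls, but the documents do not establish that. Section 6.1 also separates Moderna from Pfizer, so the planned tables would show those two responses apart whatever 3.1 says. All of this stands and limits the harm. It does not remove the conflict over who is in a primary endpoint.

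A reader might also infer that B4 Moderna recipients are certain to be counted twice. The documents do not settle this. The first endpoint in SAP 3.1 carries no in-study limit, so on its face they meet both definitions. But the second ends by specifying series given outside the study, and the SAP uses much the same phrase elsewhere for Group B4. The intended contrast may be Part A participants against B4, in which case the two endpoints do not overlap. Even so, the second endpoint would pool Moderna with other series and would not be the protocol's.

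Finally, a reader might add that series mixing Moderna with another vaccine have no assigned endpoint and that the SAP's other category is undefined. Both are true, but they are gaps in detail rather than part of this error. The protocol endpoints do not assign mixed series either, and the row in protocol Table 3 that allows "2 doses or at least 1 dose combined with an mRNA COVID-19 vaccine" sets eligibility only.

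**Conclusion.** SAP 3.1 states the wrong population for the second Part B primary neutralising-antibody endpoint when set against the protocol and against SAP 6.4.2, and the SAP does not declare the difference. Followed literally, that endpoint takes in any three-dose Moderna recipients in B4 and stops isolating the heterologous response.

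This conclusion rests on the texts and on B4 eligibility, not on any assumed number. The effect on the reported geometric mean cannot be derived. It is zero if B4 contains no Moderna recipients, and also zero if the two groups have the same geometric mean. The study is for estimation, with no between-group comparisons planned (SAP 4.2), so no error rate or power is affected. Double counting is possible on the wording but not established. The point should be fixed, and it is a contained one.

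**What to change.** Before database lock:

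- In SAP 3.1, restore the non-Moderna primary series as the population of the second Part B endpoint, and state that three-dose Moderna recipients in B4 count in the Moderna endpoint only.
- In SAP 6.1, add a pooled non-Moderna group among boosted transplant recipients, so that 6.4.2 has a row to report from.
- In SAP 4.1, return the at-least-50 minimum to the non-Moderna wording of protocol 3.1.

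If the broader population was intended, amend the protocol endpoint, bring SAP 6.4.2 into line and record the change in SAP Section 7.

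The first route costs a few lines of SAP text and one more reporting group. Protocol Table 10, footnote 17, already has earlier COVID-19 vaccine doses recorded for participants vaccinated under emergency authorisation, and SAP 6.1 already separates Moderna from Pfizer, so no new data should be needed.
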